Study Design	
This is a multicenter, open label, non-randomized study to determine the value of BreathID® C-Methacetin Breath Test System (MBT) in predicting the outcome of patients diagnosed with severe acute liver injury that is not related to acetaminophen overdose and acute liver failure who meet inclusion/exclusion criteria.
 
Informed consent will be obtained from the patient and/or patient’s legally authorized representative (LAR) or family member as defined in 21CFR50.3(m). All patients will receive medical care for severe acute liver injury or acute liver failure according to the institution’s standards of care.
 
Up to 200 evaluable patients will be consecutively enrolled. The MBT (also referred to as “Breath Test”) will be performed up to five times during the study period on all enrolled patients. An evaluable patient is one who has completed one or more Breath Tests measured for a minimum of 30 (and ideally 60) minutes after administration of the C-Methacetin solution (also referred to as “test substrate”). The first Breath Test will be performed upon admission into the study (Day 1) and repeated on Days 2, 3, 5 and 7, as close to the same time of day as possible, provided no contra-indications are present.
 
If a patient who is enrolled into the ALFSG-MBT Trial with ALI converts to ALF, breath test collection will continue until the maximum of five Breath Tests have been performed. Once the ALI patient has been enrolled into the ALFSG Registry with ALF, subsequent Breath Tests should be performed as close to the same time of day as the previous Breath Tests provided no contra-indications are present. During the initial consent process, the enrolled ALI patient should indicate consent to continue participation into the ALFSG-MBT study should the disease progress to ALF.
 
If an enrolled ALI or ALF patient receives a liver transplant, is discharged /transferred from the hospital or dies prior to Day 7, additional Breath Tests will not be performed.
 
Subjects will be contacted to determine Day 21 spontaneous survival, transplantation and occurrence of serious adverse events since the last Breath Test.
 
Only trained study personnel will perform the breath test procedure and administer the test substrate. Site principal investigators (PIs) and clinical staff will be blinded to the results of the MBT so that there cannot be any reliance on the MBT for clinical decision-making.

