### 3 INTRODUCTION

#### 3.1 Background and Rationale

The importance of identifying the patient with ALI or ALF who is likely to die without a liver transplant cannot be overstated and has remained a primary focus of clinical investigation for 25 years. A recent analysis also conducted by the Acute Liver Failure Study Group (ALFSG) found that poor outcomes in the ALI patients are less frequent than is observed in the ALF population. However, in cases where ALI was not related to an acetaminophen (APAP) overdose, progression to poor outcomes was similar: 41% of patients with non-APAP ALI progressed to ALF, transplant and/or death compared to 7% of patients with APAP ALI (1). Unfortunately, analyses have shown that the King's College Criteria (KCC) are inaccurate predictors of prognosis. Clinically based criteria such as the Sequential Organ Failure Assessment (SOFA) and Acute Physiology and Chronic Health Evaluation II (APACHE II) scores offer improved but still inadequate accuracy (2-4). These traditional scoring systems and prognostic models currently used to monitor patients with ALF lack individual sensitivity and specificity and do not provide direct information about the liver's metabolic function, which is a key variable in assessing liver status and potential disease progression versus recovery in ALF patients. The Acute Liver Failure Study Group (ALFSG) completed an analysis of predictors of outcome in the largest cohort ever studied, 1,974 patients, half of whom were randomly assigned to participate in a model development cohort, and half in a validation cohort (5). The ALFSG Prognostic Index (ALFSG-PI) identified coma grade, ALF etiology, vasopressor use, and the log transformations of admission bilirubin and INR as independent clinical predictors of spontaneous survival in patients with ALF, with a c-statistic of 0.84 by AUROC curve analysis. The ALFSG-PI was also significantly better than Model for End-Stage Liver Disease (MELD) score (0.70) or KCC (0.65). The group also developed a prognosis index for ALI patients that identified etiology, admission values of bilirubin, INR, APAP level and duration of jaundice prior to enrollment as variables associated with prediction of progression to ALF, transplant or death within 21 days (1). The ALI prognosis index had a c-statistic of 0.84. Despite these advances, better predictive modalities are still needed.

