### **3.2 Summary of BreathID® and MBT Clinical Data**

The BreathID® MBT has been used to assess the functional capacity of the liver in several clinical situations. In a study of 165 patients with cirrhosis which included two ALFSG sites, MBT predicted liver-related death and the appearance/exacerbation of ascites better than the Model for End-Stage Liver Disease (MELD) score (6, copy attached).

MBT has also been used in a pilot study of patients with ALF performed at Kings College Hospital and in Israel (7). Sixty-two patients with severe ALI/ALF of diverse etiologies were followed with the MBT during the acute phase of their illness. During their hospital course, 62% of patients spontaneously survived, 21% underwent liver transplantation, and 18% died with a mean follow-up of 7 days after baseline testing. In patients who spontaneously recovered, admission PDR and CPDR at 20 minutes after Methacetin ingestion were higher than those who died or underwent liver transplantation, with p-value of approximately 0.08 for the difference for both indices. Moreover, in the 38 patients in whom post-admission MBTs were available, PDR20 and CPDR20 were both much higher in spontaneous survivors (SS) than those who died or underwent transplant (p=0.0002 and 0.001, respectively), as were the changes in both parameters between Day 1 and Day 2-4. (The choice of the later day was not standardized. Values were used in the following order of preference depending upon their availability: Day 3, Day 4, or Day 2, if neither Day 3 nor 4 were available). Subgroup analyses clearly showed that patients who died or underwent transplant had similar PDR20 and CPDR20 on Day 1, but both were significantly lower than SS. These data strongly support the hypothesis that the MBT may assess the severity of ALF at

admission and the likelihood of hepatic recovery within 7 days of admission more accurately than laboratory tests regardless of the etiology of liver injury.

**Table 1. Methacetin breath test (MBT) results in 62 patients with ALI/ALF on admission (Day 1) and in 38 patients at one time point after admission (Day 3, or Day 2 or 4 if Day 3 is missing).**

MBT Parameter	Day	N	Total Population	Spontaneous Survivors	Death/ Transplant	P*
			Mean±SD/ Median[range]	Mean±SD/ Median[range]	Mean±SD/ Median[range]	
PDR 20	1	62	2.60[-1.71 - 33.02]	3.31[-1.71 - 13.52]	1.13[-1.22 - 12.80]	0.088

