Since current treatments used to stabilize and care for patients with ALI and ALF may obscure the main parameters used to delineate the prognosis (i.e., INR, bilirubin, grade of hepatic encephalopathy and renal/metabolic status), the MBT may show superiority over the current prognosis models. For example, INR interpretation can be confounded by blood products administered to a patient or may be impacted upon by a variety of medical interventions, such as disseminated intravascular coagulation (DIC); in contrast, the MBT is not affected by blood product administration or development of DIC. Additionally, MBT monitoring could be potentially performed every 24 hours over the patient's course in the Intensive Care Unit (ICU), providing dynamic data that may show earlier changes than routine blood tests, since it measures directly the immediate metabolism of the test substrate, as opposed to assessing the presence of blood components that have accumulated over a greater period of time, such as total bilirubin levels.

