## **11 DATA MANAGEMENT**

### **11.1 Data Handling**

The raw data from the individual tests on the BreathID® MCS device will be analyzed using Exalenz's trending software. This program provided by Exalenz will combine all tests for any given subject bearing the same identification number and will plot the trend of the breath test results with the percent change displayed. This analysis will be carried out only after the subject has completed his/her participation in the study and in order not to bias the treating physician, the results will not be shared until the study is completed.

For all other study data, sites will enter case report form data into the password protected study database housed in WebDCU™. The WebDCU™ is a validated web-based clinical trials

management system that provides the infrastructure for real-time data capture and data sharing and includes designated web servers and supporting database servers. This user-friendly web-based database system will be used for subject enrollment, data entry, data validation, project progress monitoring, user customizable report generation, and secure data transfer. The web-based data capturing system allows for study data to be directly entered into the study specific database by the site via a secure internet connection. Secure Socket Layer (SSL) is used for data encryption. The web system combines all study tools into one system which includes study database, online training and help desk, subject calendar, electronic data clarification request (DCR) process, data entry, case report form (CRF) and participate tracking system, audit trail, and report generation mechanisms. This is the system used for the currently ongoing ALFSG Registry. Clinical and laboratory data will be collected by the site in order to derive MELD, ALFSG-PI, ALI-PI and KCC scores on a daily basis. These clinical data and laboratories are mandatory as they will be needed for calculation of the clinical outcome predictor indices.

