## **12 STATISTICAL CONSIDERATIONS**

### **12.1 Sample Size**

The relationship between the Day 1 PDRPeak and clinical outcome (21-day spontaneous survival) will be assessed using logistic regression with a two-sided alpha of 0.10. Based on previous enrollment rates from the ALFSG Registry, we estimate an accrual rate of approximately 100 ALF or non-APAP ALI patients per year into the ALFSG-MBT Trial. The power of the logistic model predicting ‘good’ outcome (21 Day SS) is based on the proportion of ‘good’ outcome at the mean MBT value. Assuming this proportion is 0.50, we determined that approximately 200 enrolled non-APAP ALI and ALF patients are needed in order to ensure sufficient power (80%) to detect odds ratios of 1.5 or higher.

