### **12.2.2 Final Analyses**

Preliminary analyses will be conducted to describe the collected variables. Univariate descriptive statistics and frequency distributions will be calculated, as appropriate for all collected variables along with two-sided 95% confidence intervals. The primary endpoint, Day 1 PDRPeak will be compared between those that spontaneously survive (SS) by Day 21 and those that either die or receive a transplant by Day 21 with a logistic regression model at a two-sided alpha level of 0.10. All enrolled patients with a value at Day 1 will be included in the analysis. The primary analysis will not stratify by non-APAP ALI/ALF but exploratory analyses will be conducted that examine potential differences as described below. It is not anticipated that any enrolled patient will be missing the outcome of SS.

There are several exploratory aims that will be conducted for future hypothesis generation. In addition to the comparison of mean PDRPeak values between the two cohorts, a cutpoint for the PDRPeak value will be examined using a receiver operating curve. The identified cutpoint will be compared to other known prognostic indices including Kings College criteria (KCC), Model of End-Stage Liver Disease (MELD), and the ALFSG-PI (prognostic index). As a secondary analysis and where serial measurements are available, the trends in the MBT results (PDRPeak, PDR20, CPDR20) will be related to outcome (Day 21 SS) using repeated measures analysis. A multivariable regression will be performed to assess if PDRPeak, in combination with traditional prognostic measures provides an accurate prediction of Day 21 outcome. These pre-specified exploratory analyses will be conducted using a significance level of 0.05.

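### A significant primary odds ratio would show association, not predictive value; the planned comparison with KCC, MELD and ALFSG-PI should rest on the AUROC of continuous Day 1 PDRPeak, not on a cutpoint chosen in the same data

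*Combined protocol and SAP*

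**What the plan says.** **Primary question and test.** Sections 2 and 4.1 define the primary aim as the relationship between Day 1 PDRPeak and Day 21 spontaneous survival. Section 12.2.2 tests it by logistic regression at two-sided alpha 0.10. Section 12.1 assumes a 0.50 proportion with good outcome at the mean MBT value and concludes: "approximately 200 enrolled non-APAP ALI and ALF patients are needed in order to ensure sufficient power (80%) to detect odds ratios of 1.5" (larger ones included). It gives no unit for the odds ratio, no SD for PDRPeak and no formula.

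**Purpose.** The synopsis describes a study to determine the value of the test "in predicting the outcome of patients diagnosed with severe acute liver injury". The background in section 3.2 adds that "the MBT may show superiority over the current prognosis models".

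**Reference points.** Section 3.1 says that the King's "College Criteria (KCC) are inaccurate predictors of prognosis". It gives c-statistics of 0.65 (KCC), 0.70 (MELD) and 0.84 (ALFSG-PI) from an analysis of ALF patients.

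**Accuracy analyses.** Section 4.2.2 lists a best-distinguishing cut point as the first secondary endpoint. Section 12.2.2 derives it from a ROC curve and continues: "The identified cutpoint will be compared to other known prognostic indices including Kings College criteria (KCC"), MELD and ALFSG-PI. It also plans a multivariable regression combining PDRPeak with traditional prognostic measures. All of this is labelled exploratory, at the 0.05 level.

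**The concern.** The plan has a powered question (is Day 1 PDRPeak associated with outcome?) and a motivating question (does it predict outcome well enough to matter beside existing indices?). With 200 patients and alpha 0.10, the first can be answered yes by a marker that discriminates weakly. The second depends wholly on the exploratory comparison in section 12.2.2, and that comparison is built on a weak quantity.

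Reducing a continuous marker to one cutpoint discards most of its ranking information. Choosing the cutpoint in the same patients in whom it is then judged makes it look better than it is. The plan does not say which statistic is compared (AUROC, sensitivity, specificity or other), what criterion defines the best cutpoint, or how the comparison allows for all indices being measured in the same patients.

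At stake is the reading of the result. A significant odds ratio could be reported as prognostic value when the marker discriminates less well than KCC, and the analysis that should guard against this could itself be optimistic.

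**Working it through.** **1. The plan's own figure.** Inputs from section 12.1: OR 1.5, P = 0.50, power 80%, two-sided alpha 0.10. The unit is not given; per SD is assumed here. With b = ln 1.5 = 0.4055 and b² = 0.1644:

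- Simple formula: n = (1.645 + 0.842)² / [P(1−P)b²] = 6.18 / (0.25 × 0.1644) = 150.
- Corrected formula: δ = [1 + (1+b²)e^(5b²/4)] / [1 + e^(−b²/4)] = 1.24, and n = (1.645 + 0.842e^(−b²/4))²(1 + 2Pδ)/(Pb²) = 6.015 × 2.24 / 0.0822 = 164.
- The same formulas at alpha 0.05 give 191 and 209.
- Power at n = 200, alpha 0.10: Φ(√50 × 0.4055 − 1.645) = Φ(1.22) = 88.9% (87.5% by simulation).

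So 200 does not reproduce on the per-SD reading at alpha 0.10. It lies near the alpha 0.05 result. Alternatively it would leave room for 18 to 25% of patients without a Day 1 value ((200−164)/200 to (200−150)/200), but no such allowance is stated.

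**2. What 200 patients can detect, as an AUROC.** The rank-based approximation needs no odds-ratio unit: AUROC = 0.5 + z√[(n1+n2+1)/(12·n1·n2)], with z = 1.645 for p = 0.10 and z = 1.645 + 0.842 for 80% power.

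| Survivors / others | SE under null | AUROC at p = 0.10 | AUROC at 80% power |
|---|---|---|---|
| 100 / 100 | 0.0409 | 0.567 | 0.602 |
| 124 / 76 | 0.0422 | 0.569 | 0.605 |
| 80 / 80 | 0.0458 | 0.575 | 0.614 |

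The second row uses the pilot in section 3.2, where "62% of patients spontaneously survived, 21% underwent liver transplantation, and 18% died". The third shows 160 analysed patients. It matters because section 12.1 counts enrolled patients, section 5.2 evaluable patients, and section 12.2.2 those with a Day 1 value; the effect is small.

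Cross-check for normal data: d = 2.487 × √(2/100) = 0.352, and AUROC = Φ(0.352/√2) = 0.598.

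Skew lowers the figure. In simulations of the logistic test at n = 200, 80% power fell near AUROC 0.59 for gamma and exponential predictors and near 0.58 for a log-normal one. The p = 0.10 threshold fell near 0.560 (exponential) and 0.554 (log-normal). Table 1 in section 3.2 gives Day 1 PDR20 and CPDR20 as medians with wide ranges, so skew is plausible.

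**3. Chance of a significant primary test.** Simulated logistic Wald test, normal predictor, n = 200, alpha 0.10:

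| True AUROC | 50% survivors | 62% survivors |
|---|---|---|
| 0.55 | 34.7% | 33.3% |
| 0.57 | 53.9% | 51.7% |
| 0.60 | 81.1% | 79.0% |
| 0.65 | 98.6% | 98.1% |

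At a true AUROC of 0.60 with 50% survivors, about 87% of the significant trials show an observed AUROC below 0.65.

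**4. The cutpoint.** Take a true AUROC of 0.60 with normal groups of equal variance: d = √2 × Φ⁻¹(0.60) = 0.358. The best possible single cutpoint then has AUROC Φ(d/2) = Φ(0.179) = 0.571. That drop from 0.60 is the information lost. When the cutpoint is chosen in the same 200 patients (maximising sensitivity plus specificity), its apparent AUROC averages about 0.60 in simulation, while its true value is about 0.56 to 0.57. That gap is the optimism.

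**5. Precision available.** Hanley-McNeil SE at 100/100: 0.0399 at AUROC 0.60, 0.0387 at 0.65, 0.0368 at 0.70, 0.0344 at 0.75. Multiplying by 1.96 gives 95% half-widths of 0.078, 0.076, 0.072 and 0.067. With 0.65 treated as fixed, the interval excludes it with 80% power if the true AUROC is about 0.75.

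The paired difference depends on the correlation r between the two AUROC estimates, which the documents do not give. If both are 0.65, SE = 0.0387 × √(2−2r). The half-width is then about 0.11 at r = 0 and 0.076 at r = 0.5.

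**The case against.** **The test fits the objective.** The primary aim is association and logistic regression tests it. Any association test at this size detects effects of this order. This stands. A reader might infer that the trial is designed around an AUROC of 0.60, or is underpowered. The documents support neither: section 12.1 sets no AUROC, 0.60 is only the smallest value detectable with 80% power, and on the per-SD, normal reading 200 exceeds the number needed.

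**Accuracy is in the plan.** A reader might infer that no accuracy analysis is pre-specified. That is not so. Sections 4.2.2 and 12.2.2 pre-specify the ROC cutpoint, its comparison with three indices, and a multivariable model. The last matters because a marker with a modest AUROC alone may still add to an index. What is missing is a named statistic, a cutpoint criterion and a paired method.

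**Superiority is not an objective.** The remark about superiority is background, and discrimination is filed under hypothesis generation. This stands, so no performance threshold is being asked for.

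**The reference values are imperfect.** They come from ALF patients, whereas section 12.2.2 expects 17 to 20% non-APAP ALI. This stands and is a reason to compare within the trial's own patients.

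**200 was computed at alpha 0.05.** A reader might infer this from the arithmetic. The documents do not say so, and the unit is unknown.

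**Conclusion.** The concern holds as a gap between the primary test and the predictive reading it may be given, together with an avoidable weakness in the planned comparison. It is not a sample-size error.

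With 200 analysed patients, significance is reached near an observed AUROC of 0.57 and 80% power near a true AUROC of 0.60, somewhat lower if PDRPeak is skewed. Both lie below the 0.65 quoted for KCC, so a significant odds ratio cannot by itself show value beside the existing indices. The cutpoint comparison does not fill the gap well: at a true AUROC of 0.60 it gives up about 0.03 in AUROC and then appears to regain it through optimism.

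Assumptions: a Day 1 value for all 200, 50 to 62% survivors, and a roughly normal PDRPeak except where skew is stated. The section 3.1 values are reference points only. The missing odds-ratio unit and the unexplained 200 are minor clarifications.

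**What to change.** Keep N, alpha, the primary test and the primary endpoint.

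**Section 12.2.2**
- Base the comparison with other indices on the AUROC of continuous Day 1 PDRPeak with its 95% CI. State the expected half-width: about 0.07 to 0.08 at 200 for AUROCs of 0.60 to 0.75.
- Add the paired AUROC difference from KCC, MELD and ALFSG-PI in the same patients, with its 95% CI (for example by the DeLong method).
- Report the data-derived cutpoint as descriptive, or with an optimism correction, and name the criterion that selects it.
- State that a significant odds ratio alone will be reported as association.

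**Section 12.1**
- State the unit of the odds ratio, the formula, and the basis for 200, including any allowance for missing Day 1 values. Say whether 200 means enrolled, evaluable or with a Day 1 value.

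**Cost.** A few sentences and a little extra analysis, with no more patients, tests or data. Section 11.1 already says of the index inputs: "These clinical data and laboratories are mandatory as they will be needed for calculation of the clinical outcome predictor indices". The other price is a more modest conclusion if the marker discriminates weakly.

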### **12.2 Statistical Analyses**

#### **12.2.1 Futility Analysis**

A futility analysis will be conducted after 100 consecutive enrollments with 21-day outcome obtained. This analysis is based on the error spending function method with O'Brien and Fleming (OBF) type stopping guidelines. The goal of this analysis is to consider stopping the study early if there is no signal of a difference in the PDRPeak distributions between those that SS at 21 days

and those that do not SS. If the p-value of a two-sided t-test for the difference in means at an alpha level of 0.10 is 0.807 or greater, then the study may be considered stopped for futility.

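### Is the futility cut-off of p ≥ 0.807 inconsistent with the 80%-power design, and is it wrong to ignore the direction of the effect?

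*Combined protocol and SAP*

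**What the plan says.** Section 12.1 sets out the design. The relation between Day 1 PDRPeak and 21-day spontaneous survival "will be assessed using logistic regression with a two-sided alpha of 0.10". The stated aim is "sufficient power (80%) to detect odds ratios of 1.5 or higher", with a spontaneous survival proportion of 0.50 at the mean breath test value, and "approximately 200 enrolled non-APAP ALI and ALF patients are needed".

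Section 12.2.1 adds one interim look: "A futility analysis will be conducted after 100 consecutive enrollments with 21-day outcome obtained". It names error spending with O'Brien-Fleming-type guidelines and gives the purpose: "The goal of this analysis is to consider stopping the study early if there is no signal of a difference". The trigger is worded as follows: "If the p-value of a two-sided t-test for the difference in means at an alpha level of 0.10 is 0.807 or greater". Stopping is permitted in that case, not required.

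Section 12.2.2 keeps the final test two-sided at 0.10. Section 4.1 frames the primary question as whether mean PDRPeak differs between spontaneous survivors and patients who die or are transplanted. It names no direction.

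**The concern.** The cut-off looks too lenient. A widely used O'Brien-Fleming-type spending formula, applied to beta = 0.20 at half the information, gives a p-value near 0.67 to 0.70. On that basis 0.807 would seem to belong to a design with higher power, and the rule would stop a worthless test less often than intended.

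The second worry is direction. The breath test is useful if a higher PDRPeak goes with survival. A rule on the two-sided p-value stops a slightly favourable interim result (z = +0.24) but continues a clearly unfavourable one (z = −1.5, p = 0.13). If that were an oversight, a further 100 critically ill patients could be tested when the hoped-for answer was already out of reach.

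**Working it through.** **1. Inputs.** From 12.1: two-sided alpha 0.10 (critical value 1.645), power 80% (beta 0.20), N about 200. From 12.2.1: look at 100, so information fraction t = 100/200 = 0.5; bound on a two-sided p-value. Assumed: the futility rule is non-binding, consistent with the permissive wording, so the final critical value stays at 1.645.

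**2. Reproducing 0.807.** The two-sided O'Brien-Fleming-type spending function is 4[1 − Φ(z(1−β/4)/√t)].

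- β/4 = 0.05, z = 1.645, and 1.645/√0.5 = 2.326. The upper tail is 0.0100, so 4 × 0.0100 = 0.0400 of beta is spent at the look.
- Solve P(\|Z1\| < b) = 0.0400 jointly with overall power 0.80. The solution is a final drift of 2.532 and b = 0.2437.
- Check: interim drift = 2.532 × √0.5 = 1.790. Φ(0.2437 − 1.790) − Φ(−0.2437 − 1.790) = 0.0610 − 0.0210 = 0.0400.
- Two-sided p = 2[1 − Φ(0.2437)] = 0.8075. The plan says 0.807.

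**3. Where the apparent mismatch comes from.** The other common form, 2[1 − Φ(z(1−β/2)/√t)], uses 1.2816/√0.5 = 1.812 and spends 0.0699. It gives b = 0.431, p = 0.667 when solved jointly with power, or b = 0.391, p = 0.696 at the fixed-sample drift 1.645 + 0.842 = 2.486. Section 12.2.1 does not say that this form was used. The two-sided form suits a two-sided test and returns the stated number at the stated power.

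**4. What the rule does.** The stated cut-off is \|z\| ≤ 0.244. For N = 200, I assume that the odds ratio is per standard deviation of PDRPeak and that outcomes split evenly; 12.1 gives no unit for the odds ratio. The final drift at OR 1.5 is then ln(1.5) × √(200 × 0.25) = 0.4055 × 7.071 = 2.867. The last two columns apply the same bound to the signed statistic (stop if z < 0.244) and keep the final test two-sided.

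| True effect | Stop, stated rule | Power, no look | Power, stated rule | Stop, signed rule | Power, signed rule |
|---|---|---|---|---|---|
| None (OR 1) | 19.3% | – | – | 59.7% | – |
| OR 1.5 | 2.6% | 88.9% | 87.9% | 3.7% | 87.7% |
| OR 1/1.5 | 2.6% | 88.9% | 87.9% | 98.8% | 0.2% |

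At the fixed-sample 80%-power drift of 2.486 the stated rule stops 4.2% of the time, and power falls from 80.0% to 78.7%.

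**5. Does it rank interim results wrongly?** Given Z1 = z, the final statistic has mean z√t + θ(1 − t) and standard deviation √(1 − t). Under the observed trend, θ = z/√t, so the mean is 1.414z. The chance of a significant final two-sided test, counting both tails, is:

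| Interim z | Two-sided p | Rule | Conditional power |
|---|---|---|---|
| +0.244 | 0.807 | may stop | 3.6% |
| −1 | 0.32 | continue | 37% |
| −1.5 | 0.13 | continue | 75% |
| −2 | 0.046 | continue | 95% |

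For the two-sided question that the plan asks, the rule stops where a significant result is least likely. The order reverses only if success is limited to one direction and OR 1.5 is still taken as true after a negative interim result: 48% at z = +0.244, 10% at −1, 3.6% at −1.5. Under OR 1.5, however, an interim z below −1 has probability 0.12%, and below −1.5 it has 0.02%.

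**The case for a change.** The strongest case concerns direction. The pilot data in 3.2 show higher Day 1 values in spontaneous survivors, and 12.1 powers for odds ratios of 1.5 or more for the good outcome. A lower PDRPeak in survivors would contradict the rationale for the test, and nothing in the plan says that such a finding is worth another 100 patients. A signed rule would cost only 0.2 points of power at OR 1.5 (87.9% to 87.7%) and would stop a worthless or reversed test far more often.

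These figures are right, and a team interested in one direction only could reasonably choose a signed rule. The price is elsewhere: the study would stop 60% of the time under no effect and would almost never establish a reversed association, although the final test is kept two-sided to allow for one. The later patients also serve the aims in 12.2.2: cut-point, serial trends, multivariable prediction, and a non-APAP ALI subgroup expected to number only 35 to 40. Because stopping is advisory, a p-value below 0.807 does not oblige anyone to continue after a clearly reversed result.

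It also stands that 12.2.1 names neither the spending function nor the beta spent, and does not say how a reversed interim effect should be handled. A reader has to reconstruct 0.807. That is missing detail; it does not make the figure wrong.

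**Conclusion.** The concern does not hold. The cut-off of 0.807 follows from the plan's own alpha, power and timing (recomputed 0.8075). The match rests on the two-sided O'Brien-Fleming-type spending form, a non-binding rule and a look at exactly half the information; the first two are not written out in 12.2.1. Ignoring direction is consistent with a non-directional objective, a two-sided final test and a look meant to detect the absence of any difference. The rule costs 1.3 points of power at the 80%-power effect, and about 1 point at N = 200 with an odds ratio of 1.5 per standard deviation (assumed unit). A signed bound is a legitimate alternative with its own costs, so choosing it is a matter of preference and not a needed correction.
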